
Reporting-order: Plain Film - ULDC
 
The plain film of half the participants (randomized) will be submitted for reporting by a radiologist as a first imaging method. After finishing this report, the same radiologist will assess the ULDC of this participant. In this second report, the findings of both examinations will be summarized, and a second report will be filed.
 
Emergency physicians will first receive the report for the plain film of the chest and will be asked for the diagnosis and its probability. Next, the report for ULDC will be presented to them. Again, diagnosis and probabilities will be documented.
	
Diagnostic Test: ULDC
 
Ultra-Low-Dose-CT (ULDC) of the chest using tin filters with third-generation dual-energy CT devices. The projected dose used will be approximately 0.2 mSv per ULDC of the chest.

Reporting-order: ULDC - Plain Film
 
For half the participants (randomized) radiologists will first receive the data from ULDC of the chest and write a report. Subsequently, they will receive the data from the plain film of the chest and may expand their report (explicitly separated).
 
Emergency physicians will first receive the report for the ULDC of the chest and will be asked for probabilities of the nine most frequent diagnoses in chest-imaging plus "other". Next, they will be presented with the report for the plain film and will again be asked to give an estimation of the probabilities for the same diagnoses as before.
	
Diagnostic Test: ULDC
 
Ultra-Low-Dose-CT (ULDC) of the chest using tin filters with third-generation dual-energy CT devices. The projected dose used will be approximately 0.2 mSv per ULDC of the chest.

6 Hypotheses and outcome measures

Null hypothesis:

- There is no difference in accuracy between ULDCCT of the thorax and plain film of the thorax regarding the primary diagnosis.

Alternative hypothesis:

- ULDCCT of the thorax offers higher accuracy than plain film of the thorax regarding the primary diagnosis.

Primary Outcome Measure:

Accuracy of ultra-low-dose-CT of the chest and plain film of the chest

Description:

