Initial radiologic diagnostic accuracy of both methods will be assessed by analyzing the number of reports that are changed after the images of the second modality become available to the radiologist in Arm 1 compared to Arm 2.

In a final approach, the diagnostic accuracy will be analyzed by retrospectively comparing all reports with the gold standard, which will be built from all available patient data at the end of the study, including all follow-up imaging studies and laboratory tests.

Secondary Outcome Measures:

- Sensitivity and specificity in ULDCT and plain film
- Frequency of change in radiological diagnosis
- Frequency of change in emergency physician's diagnosis
- Frequency of change in (planned) therapeutic course of action by emergency physician
- Frequency of accidental diagnosis in ULDCT of the chest and plain film of the chest
- Frequency of additional diagnostic imaging needed
- Frequency of unclear reports in ULDCT and plain film
- Diagnostic confidence in ULDCT and plain film by radiologist
- Diagnostic confidence in ULDCT and plain film by emergency physician

7 Inclusion criteria

Sex	All
Gender-based	No
Age limits	Minimum: 18 years Maximum: 92 years
Accept healthy volunteers	No
Participants	All patients who are assigned to a clinically indicated chest X-ray by the emergency department of Vienna General Hospital
Consent	Ability to provide informed consent Informed consent after detailed patient briefing

8 Exclusion criteria

Clinical status	A critical clinical condition that does not allow the examination with both modalities (ULDCT of the chest, chest X-ray)
Assignment	Assigned to chest X-ray as follow-up
Pregnancy	Women with positive β -HCG-test

9 Ethical considerations

- The mean effective dose of a chest X-ray examination in two views (pa, lat) is 0.08 mSv (Wachabauer and Röthlin 2017).
- The targeted mean effective radiation dose for one thoracic ultra-low-dose-CT (ULDCT) is approx. 0.2 mSv. This corresponds to approximately one month of natural background radiation in Austria. Compared to standard-dose CT examinations, ULDCT of the thorax causes about one-twentieth to one-fortieth of effective radiation dosage. Therefore, its dosage is much closer to a chest X-ray in two views than to a standard-dose CT, or even a low-dose CT examination.
- Even the cumulative dose of both examinations comes with a negligible radiation dose. Thus, no negative effects are to be expected.

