This will involve a multi-reader analysis by four radiologists in training and four specialists. All eight physicians will independently read and report all examinations by means of structured reporting. The reading time is not specified. Two groups with all 300 patients each will be created: In the 1st group, the chest X-ray examinations of Pts. 1-150 and the Ultra-Low-Dose-CT examinations of Pts. 150-300 will be available. In the 2nd group, this will be reversed. All patients will be fully anonymized and randomized. Two radiologists in training and two specialists will first read and report on group 1, the other four doctors will first read and report on group 2. Between the evaluations of group 1 and group 2 there will be at least one month to prevent a possible recognition of a case.

The gold standard will be built from all available patient data at the end of the study, including the results of all imaging procedures, follow-up examinations, physical medical examinations, laboratory and histopathological tests and further diagnostic procedures (concerns all available data, regardless of whether the patient is admitted as an inpatient).

The structured findings are then compared with the gold standard to determine the accuracy, sensitivity and specificity of both procedures.

Documentation:

- Waiting time for the ULDCT will be logged.
- Waiting time for the X-ray will be logged.

14 Statistical analysis plan

Power and sample size:

A total of 250 participants is targeted.

This is based on the following assumptions:

- Accuracy of a chest X-ray is 80%
- Accuracy of a ULDCT of the chest is 93%
- Dropout rate is 20% (one in five potential participants)

According to calculations using NQuery Advanced (version 8.3.0.0), 123 participants per arm (total of approx. 250 participants) will be required to reach a power of 85% in a one-sided test (alpha 2.5%). Due to the assumption of a dropout rate of 20% (approx. one in five potential participants), a sample size of 300 is required.

Cross tabulation and χ^2 -tests will be used to compare percentages (e.g., accuracy, sensitivity, ...). Diagnostic confidence will be compared by applying a Mann-Whitney U test.

15 Compensation

None.

Participants will not receive any compensation.

16 Study suspension

Since no negative effects on patients are expected, the trial will be suspended or stopped only if it becomes obvious that ultra-low-dose-CT examinations do not offer any benefit.

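### Emergency-physician confidence is elicited with different questions in the two arms, and the plan does not say which rating enters the Mann-Whitney test

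*Combined protocol and SAP*

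**What the plan says.** Section 6 lists two confidence outcomes among the secondary measures: "Diagnostic confidence in ULDCT and plain film by radiologist" and "Diagnostic confidence in ULDCT and plain film by emergency physician". Neither has a scale, a direction or a scoring rule. Section 14 adds only this: "Diagnostic confidence will be compared by applying a Mann-Whitney U test". It does not name the variable, the unit of analysis or the groups compared.

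Section 5 describes what the emergency physician records.

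- **Plain film first (Arm 1).** First step: "Emergency physicians will first receive the report for the plain film of the chest and will be asked for the diagnosis and its probability". Second step, after the ULDCT report: "Again, diagnosis and probabilities will be documented".
- **ULDCT first (Arm 2).** First step: physicians "will be asked for probabilities of the nine most frequent diagnoses in chest-imaging plus" a tenth category, 'other'. Second step, after the plain-film report: they "will again be asked to give an estimation of the probabilities for the same diagnoses as before".

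In Arm 1 the radiologist's second report is itself a joint one: "In this second report, the findings of both examinations will be summarized, and a second report will be filed".

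**The concern.** If the stated probabilities are the confidence measure, two things stand in the way of a clean comparison of plain film with ULDCT.

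First, the arm fixes both the modality seen first and the question asked first. A physician who names one diagnosis and rates it is doing a different task from one who spreads probability over ten listed items. Any difference between first ratings could come from either source, and no analysis can fully separate them, because no patient has plain film first with the ten-item question or ULDCT first with the single one.

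Second, every second rating is made by a physician who has already seen the other modality's report. It measures confidence after both examinations. It also comes from the same patient as the first rating, and a Mann-Whitney test assumes independent samples.

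What is at stake is the interpretation of one secondary outcome, not the primary accuracy comparison.

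**Working it through.** The plan gives no figure for this outcome, so there is none to reproduce. The 123 per arm in Section 14 concerns accuracy, and nothing below depends on it.

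**1. Which ratings can be compared**

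| Rating | Reports seen | Question described |
|---|---|---|
| Arm 1, first | plain film | named diagnosis and its probability |
| Arm 1, second | both | diagnosis and probabilities, list not specified |
| Arm 2, first | ULDCT | nine diagnoses plus 'other' |
| Arm 2, second | both | same ten items |

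Only the two first ratings are single-modality. They come from different, randomized patients, so they are the independent groups that a Mann-Whitney test needs. They are also the two rows where the question differs.

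**2. How large a form effect would matter**

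Assumptions: 250/2 = 125 patients per arm, one value per patient, equal modalities, normally distributed values, and a form effect that shifts one arm by d standard deviations. The critical value is 1.96, matching the one-sided 2.5% used in the sample size.

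- Standard error of P(ULDCT value > plain-film value) under no difference: √[(125 + 125 + 1)/(12 × 125 × 125)] = √(251/187,500) = 0.0366.
- Significance threshold: 0.5 ± 1.96 × 0.0366 = 0.5 ± 0.072.
- A shift d gives P = Φ(d/√2). Setting P = 0.572 gives d/√2 = 0.181, so d = 0.26.

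A form effect of about a quarter of a standard deviation would thus produce a significant difference about half the time. Whether the real effect is smaller or larger cannot be told from the documents.

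**3. How much the undefined variable matters**

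Illustrative simulation, with assumptions that are not in the documents: 125 patients per arm, ten categories, one true diagnosis per patient, softmax probabilities with separation 2 for plain film and 3 for ULDCT, noise SD 0.5, 300 runs. The mean highest probability is then 0.43 for plain film and 0.66 for ULDCT, so ULDCT is the more decisive test.

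| Value ranked | P(ULDCT > plain film) |
|---|---|
| Highest probability, one per patient, both arms | 0.91 |
| All ten raw values pooled, both arms | 0.30 |
| Arm 1 single value against Arm 2 ten values | 0.09 |
| As the row above, but equal modalities | 0.05 |

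The last two rows follow from arithmetic. Nine of the ten Arm 2 values are non-leading and fall below the Arm 1 leading value. The tenth exceeds it with probability 0.91, or 0.50 if the modalities are equal: 0.1 × 0.91 = 0.09 and 0.1 × 0.50 = 0.05. With equal modalities the answer should be 0.50.

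The pooled result reverses because a confident exclusion is a low number. Ranking p = 0.01, 0.30, 0.50, 0.70 and 0.99 gives 1 to 5, with the near-certain exclusion lowest.

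**4. A limit of the highest probability**

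A second illustration uses mean item probabilities of 0.90 (present) and 0.05 (absent) for the sharper test, and 0.70 and 0.15 for the vaguer one. The highest raw probability gives P = 0.96 when every patient has one of the ten diagnoses, but 0.49 when half have none. Section 10 recruits regardless of indication, so patients without an acute finding are to be expected. The highest probability works only if a category covers them.

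**The case against.** A reader might infer that the planned test scores a confident exclusion as the lowest confidence, and so would report the better modality as the worse one. The documents do not support that. Section 14 names a test and no input. Nothing says that raw item probabilities are ranked, or that ten correlated values per patient are pooled. The probability of a named or leading diagnosis does rise with confidence when a diagnosis is present, and ranking it gives the right direction (0.91). The reversal is one consequence of an undefined variable, not a rule in the plan.

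Other points on the plan's side:

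- No section says that the probabilities are the confidence score. No instrument is described for radiologists either, so a separate rating scale may exist outside this document. This stands as a caveat.
- The Arm 1 wording may be shorthand for the same ten-item form; its second step does speak of probabilities in the plural. That is possible, but the text as it stands describes different questions, and one sentence would settle it.
- The plan does not say that second ratings enter the modality comparison, and the Mann-Whitney test suits the first ratings. This stands: the test need not change.
- Confidence is a legitimate outcome whether or not the physician is right, so the absence of a score against the gold standard is not an error. Nor is distance from 50% a safe substitute: with ten categories, complete ignorance is p = 0.10 each, and 2 × |0.10 − 0.50| = 0.80 would read as 80% certain.

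**Conclusion.** The point holds as one of specification and data collection. As described, the first question differs by arm, so a first-rating comparison confounds modality with form. The second ratings are confidence in neither modality and are paired with the first. The variable entering the test is undefined, and admissible choices can give different answers from the same data.

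This rests on taking the Section 5 wording at face value and on probability being the confidence measure, as it is the only candidate described for emergency physicians. The size of the form effect is unknown. The quarter-SD figure and the simulated probabilities show sensitivity under stated assumptions and do not predict the result. The severity is low: it concerns a secondary outcome, and the repair is cheap.

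**What to change.** - **Section 5:** collect the same ten probabilities in both arms at both steps, and make sure that one category covers the absence of an acute finding.
- **Section 14:** state that emergency-physician confidence is one value per patient, for example the highest stated probability. Compare it by the Mann-Whitney test between first-report ratings only, plain film in Arm 1 against ULDCT in Arm 2. Report second-report ratings separately, as confidence after both examinations.
- **If a separate confidence scale is in use:** name it in Section 6, with its range and direction, and apply the same first-report rule.
- **Optional:** a Brier score against the gold standard as a supplementary measure of accuracy, not as a replacement for confidence.

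The cost is a longer first-step form in Arm 1 and a few lines of SAP text. Second ratings leave the modality comparison, so each modality is rated in half of the patients.
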